# 6.3. Measures to Minimize Bias: Randomization and Blinding

This is a double-blind study. Eligible participants who meet all inclusion and no exclusion criteria will be assigned unique numbers for enrollment and randomization.

On Day 1 participants will be assigned a unique number (randomization number) in ascending numerical order. The randomization number encodes the participant's assignment to one of the 6 cohorts of the study, according to the randomization schedule generated prior to the study by the Statistics Department at Syneos Health.

Participants will be randomly assigned in a 6:2 ratio to receive either single or multiple doses of ALXN1830 or PBO (Table 14). The Investigator will remain blinded to each participant's assigned study drug throughout the course of the study. In order to maintain this blind, site's pharmacy staff will be responsible for the reconstitution and dispensation of all study drug.

In the event of a Quality Assurance audit, the auditor(s) will be allowed access to unblinded study drug records at the site(s) to verify that randomization/dispensing has been done accurately.

In the event of an emergency, an envelope for each participant containing his/her study drug assignment will be available in the pharmacy at the clinical study site. Unblinding should only be considered for the safety of the participant. If unblinding is deemed necessary by the Investigator, the Investigator can unblind the participant's treatment allocation using the envelope available from the pharmacy staff. The Investigator must note the date, time, and reason for unblinding. The Investigator should inform the Medical Monitor that the participant was unblinded; however, the Investigator should not reveal to the Medical Monitor the participant's treatment allocation. The blind will be maintained for persons responsible for the ongoing conduct of the study (such as the management, monitors, Investigator) and those responsible for data analysis and interpretation of results at the conclusion of the study, such as biometrics personnel. Unblinded information will only be accessible to those who need to be involved in the safety reporting to health authorities, independent ethics committees (IECs), or persons performing ongoing safety evaluations during the study. The Investigator will receive only blinded information unless unblinded information is judged necessary for safety reasons.

# **6.4.** Study Intervention Compliance

Participants will receive study drug directly from the Investigator, under medical supervision. The date and time of each dose administered in the clinic will be recorded in the source documents and recorded in the CRF. The dose of study drug and study participant identification will be confirmed at the time of dosing by a member of the study site staff other than the person administering the study drug.

# 6.5. Concomitant Therapy

Any medication or vaccine (including over-the-counter or prescription medicines, vitamins, and/or herbal supplements, or other specific categories of interest) that the participant is receiving at the time of enrollment or receives during the study must be recorded along with:

- · Reason for use
- Dates of administration including start and end dates
- Dosage information including dose and frequency

Concomitant treatment that is medically indicated for any AEs the participant experiences during the study is permitted.

If concomitant medication is needed during the study, this medication must be recorded on the eCRF, stating its generic name, time of administration, dose, route and duration, as well as the reason for administration

The Medical Monitor should be contacted if there are any questions regarding concomitant or prior therapy.

# 6.5.1. Hydration

It is recommended that study participants drink approximately 2 L (women)/2.5 L (men) of water every day during the 3 days preceding and following an infusion treatment (further information on hydration prior to dosing is provided in Section 10.7.2).

### 6.5.2. Supportive/Symptomatic Care

The use of supportive therapy/symptomatic treatment is allowable at any time during the study to treat AEs. The date and time of administration of supportive therapy/symptomatic treatment as well as the name and dosage regimen of any medication must be recorded. Details are provided in the study manual.

Supportive/symptomatic care such as histamine H1 and H2 receptor blockers, eg, diphenhydramine and famotidine are recommended for any manifesting allergic reactions and associated gastrointestinal symptoms; ondansetron for persistent nausea; bronchodilators for potential dyspnea, eg, salbutamol or pirbuterol; analgesics/antipyretics for headache, pyrexia and myalgia, eg, acetaminophen; and fluids or normal saline in case of hypotension.

Adhere to infectious disease preventive measures per World Health Organization (WHO) and local guidance. If a participant develops any signs or symptoms suggestive of infection (any), they should be treated as per the relevant local guidelines.

#### 6.5.3. Vaccinations

To mitigate the potential of sinopulmonary infections associated with anti-FcRN targeted IgG reduction therapy, all participants in this study must have been adequately vaccinated against the following:

- 1. Pneumococcus
- 2. Seasonal influenza

#### 6.5.4. Antibiotics Use

Antibiotics may be administered as needed to manage infection.

#### **6.5.5.** Disallowed Medication

During the study, participants are not allowed to use any kind of prescribed medication, including mAbs other than the study drug, any investigational drug or device, and vaccinations within 2 weeks of screening (other than those to be administered as part of this study; refer to Section 6.5.3) and for the duration of the study.

The use of over-the-counter medication is not allowed from 14 days prior to the first administration of study drug until the end of study (EOS) except the medications described above.

### 6.6. Dose Modification

Decisions to continue or modify dosing will be made by the Investigator and/or SRC after review of the blinded data. The SRC may also make recommendations regarding safety issues, study conduct, or study suspension.

# 6.7. Intervention After the End of the Study

This is a healthy participant study and no follow-up study drug administration is planned.

# 7. DISCONTINUATION OF STUDY INTERVENTION AND PARTICIPANT DISCONTINUATION/WITHDRAWAL

# 7.1. Discontinuation of Study Intervention

In rare instances, it may be necessary for a participant to permanently discontinue (definitive discontinuation) study drug. Unless a participant fully withdraws their consent, they will continue their enrollment without study drug administration but will be required to complete a follow up visit for safety purposes. See the SoA (Section 1.3) for data to be collected at the time of discontinuation of study drug and follow-up and for any further evaluations that need to be completed.

# 7.2. Stopping Criteria

#### 7.2.1. Immunoglobulin Stopping Rules

It is proposed that the lower limit of IgG will be set at  $\leq 300$  mg/dL as an individual stopping rule for the healthy participant study. More specifically, if any predose measurements show a reduction of IgG level to  $\leq 300$  mg/dL, the individual stopping rule will be met. Repeat testing to confirm the consistency of the result is permitted. Healthy participants can rebound to their baseline IgG level when the drug is discontinued because they are not immunocompromised, as evidenced by existing anti-FcRn studies. Additionally, risk mitigation strategies such as antibiotics or IVIG replacement therapy may be implemented if participants have laboratory evidence of infection and/or are clinically symptomatic.

If 2 or more participants in a cohort exhibit IgG reduction to  $\leq 300 \text{ mg/dL}$ , dosing in that cohort/dose level will stop and no further dose escalation will occur.

In addition, any participant for whom IgA or IgM falls below the normal limits (according to the reference ranges of the laboratory) and is associated with clinical signs and symptoms will be discontinued from further dosing.

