## 4.2. Scientific Rationale for Study Design

ALXN1830 has been studied in 5 clinical studies, 4 studies using the IV route of administration and one SC administration. Refer to Section 2.2 for background on clinical studies conducted with ALXN1830 to date.

This randomized, double-blind, PBO-controlled, SAD/MAD design was chosen for assessment of the safety, tolerability, PK/PD, and immunogenicity of single- and multiple ascending doses of ALXN1830 administered SC.

Healthy participants are the appropriate population for this study, enabling the effects of ALXN1830 to be evaluated without the potential confounding effects of other disease activities, comorbidities, or medications.

A staggered dosing paradigm is being used for participant protection. A PBO control is implemented in each cohort. Due to the difficulty of providing a matching PBO, participants randomized to PBO will receive an equivalent volume of saline at the same SC infusion rate as the active treatment.

ALXN1830 is an anti-FcRn mAb that blocks recycling of IgG antibodies, reducing the total IgG in circulation, including potentially pathogenic IgG autoantibodies associated with multiple autoimmune diseases. Thus, reduction in IgG level is used to measure the anti-FcRn PD activity of ALXN1830.

This study uses a comprehensive approach to minimize the potential risk of infection in the healthy participants due to the theoretical concerns associated with reducing total IgG (discussed in greater detail in Section 10.6). The following criteria will be observed as part of the enrollment criteria (Section 5.1), monitoring, and specified response to certain signs, symptoms, or laboratory results:

- Inclusion criteria of heathy participants with:
  - Immunoglobulin G levels of  $\geq 1,000 \text{ mg/dL}$
  - No history of acute and chronic infections, ie, enrolled healthy participants will be immunocompetent
  - Absence of any immunologic deficiencies, as per the Investigator's discretion
  - Pneumococcus and seasonal influenza vaccination
- To ensure a timely and adequate intervention if needed, IgG levels will be continuously and closely monitored during this study.
- Stopping rules (Section 7.2) for individuals and cohorts will be based on reduction of IgG level to ≤ 300 mg/dL (justification for IgG level to ≤ 300 mg/dL is provided in Section 10.6).
  - Dosing will be permanently stopped in any individual if the IgG level is reduced to ≤ 300 mg/dL.

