c AUCSC = (Dose/CLIV) \* F, where CLIV is scaled as CLIV = (Median CLIV) × (body weight/median body weight)0.75. Median CLIV at 10 mg/kg = 239 mL/h with a median body weight of 82.7 kg (SYNT001-101); Median CLIV at 20mg/kg = 215 mL/h with a median body weight of 79 kg (SYNT001-104); Median CLIV at 30 mg/kg = 154 mL/h with a median body weight of 75.8 kg (SYNT001-101). Where median CLIV is not available at certain dose levels (eg 15 mg/kg), doses (mg/kg) are round up to obtain a conservative estimate. Median CLIV for 45 mg/kg is set to equal to median AUCIV at 30 mg/kg (2.03 mL/h/kg). The AUC represents AUC0-inf and AUCss for single and multiple doses respectively.

<sup>d Safety margin = (Monkey NOAEL in mg/kg) / (Human dose in mg/kg). Monkey NOAEL for weekly dosing is 100 mg/kg (Studies 2455-024 and 2455-016).

<sup>e Safety margin = (Monkey AUC0-120h at NOAEL) / (Predicted human AUCSC). Day 29 AUC0-120h =  $6420 \text{ h*}\mu\text{g/mL}$  at 100 mg/kg weekly SC (Study 2455-024).

f Safety margin = (Monkey AUC0-Tlast at NOAEL) / (Predicted human AUCSC). Day 92 AUC0-Tlast = 34800 h\*μg/mL at 100 mg/kg weekly IV (Study 2455-016).

<sup>g IgG reduction is based on predicted IgG reduction at equivalent IV dose in mg/kg. IgG reduction at median body weight is presented.

participant) or 24-fold (for a 75-kg participant) based on the NOAEL exposure from the 27-week IV monkey toxicity study. More importantly, a 30 mg/kg IV single dose has been tested in healthy participants and this starting dose of 1500 mg SC is expected to be roughly one-fifth to one-eighth of the exposure at 30 mg/kg IV, based on the low bioavailability observed in monkeys for ALXN1830 and in healthy participants from other anti-FcRn compounds. Based on these observations, the expected maximum IgG reduction at 1500 mg SC would be around -45% from baseline.

In the SAD portion, the SC dose will be escalated 1.5-fold from 1500 mg (Cohort 1) to 2250 mg (Cohort 2). An SRC review of safety, tolerability, and IgG data will be conducted before each dose escalation. Staggered dosing and pre-specified stopping rules based on safety and IgG reduction will be implemented in all cohorts.

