As shown in Table 16 the first MAD cohort will be administered 750 mg SC qw for 12 weeks (Cohort 3). On a mg/kg basis, the 750 mg SC qw dose represents at least a 7 to 35-fold safety margin when compared to the NOAEL exposures of the 5-week SC and 27-week IV monkey GLP studies. The first MAD cohort (750 mg, qw, Cohort 3) may start at the same time as the single-dose Cohort 1 (1500 mg) while the rest of the MAD cohorts will start after SRC review of the previous MAD cohorts. While all the MAD cohorts have a treatment duration of 4 weeks, Cohort 3 (750 mg SC qw for 12 weeks) is of an extended duration to enable the evaluation of immunogenicity and safety after long term administration of ALXN1830.

The SC multiple doses will be escalated 2-fold from 750 mg qw to 1500 mg qw (Cohort 4), and then 1.5-fold to 2250 mg qw (Cohort 5) after SRC review. At these dose levels, the expected maximum IgG reduction after 4 qw doses is expected to be around 69% and 72%, respectively, which is similar to that observed with 20 mg/kg IV in Study SYNT001-104 (after the 3 qw loading doses).

As shown in Table 15, Cohort 6 will assess the safety, tolerability, PK, PD, safety, and immunogenicity of ALXN1830 in Japanese participants at the highest tolerable dose established in the non-Japanese participants (ie, either up to 1500 mg or up to 2250 mg SC qw for 4 doses). The exact dose and time of dosing will be determined after SRC review of all safety data through Day 36 from Cohort 5 as well as from all prior cohorts. Japanese participants are expected to have a lower mean body weight than non-Japanese participants. This and other differences (eg, genetics) may impact PK/PD in Japanese participants. Although Japanese participants may potentially have slightly higher exposure based on the lower mean body weight, the overall exposure in Japanese participants is predicted not to exceed established safety margins.

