The lack of infection risk following anti-FcRn treatment is likely due to both the specificity and transient nature of the IgG reduction, which returns to baseline relatively rapidly after discontinuation of treatment. Specifically, in a single dose and 4-week multiple dose study of the anti-FcRn antibody M281 in healthy participants (n = 50), tIgG was reduced by 85% compared to baseline, and at least 50% of participants experienced a decrease of IgG to < 200 mg/dL over the 2 highest SAD and both MAD cohorts, with no SAEs and few moderate AEs. The incidence of infection-related AEs in this study was similar between the drug-treated groups and PBO, and IgG levels returned to within 20% to 25% of baseline levels within 56 days (Ling, 2019).

Similarly, in a 4-week multiple dose study in healthy participants (n = 62) using the anti-FcRn, efgartigimod, tIgG was decreased on average by approximately 75%, with some individuals showing reductions of up to 85%. There was no increase in infections due to efgartigimod treatment, and IgG levels returned to baseline within 8 weeks after the last dose (Ulrichts, 2018). Also, in a SAD study in healthy participants (n = 48) of the anti-FcRn, rozanolixizumab, IgG levels were reduced by up to 47.6% and returned to baseline within 57 days post dose, with little or no TEAEs reported (Kiessling, 2017). Recently, in a SAD and 4-week MAD study of RVT-1401, total IgG was reduced by up to > 75%, with all AEs being mild to moderate in severity and no participants requiring premature discontinuation due to AEs (Collins, 2019).

Finally, in the previous SAD and MAD studies of ALXN1830 in healthy participants, an IgG lowering of up to 64% was observed (in the 20 mg/kg MAD cohort) with no increased risk of infection, and the IgG levels returned to baseline levels 43 days after the last dose. In total, studies with 5 different anti-FcRn therapeutics (M281, efgartigimod, rozanolixizumab, RVT-1401, and ALXN1830) in well over 200 healthy participants have generally shown no increased risk of infection, and there have been no cases of severe or serious infections reported following anti-FcRn treatment.

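### Section 7.2.1 ties the individual IgG stop to predose samples, Section 4.2 and the cohort rule do not, and no IgG check is required before an infusion (minor)

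*Protocol*

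**What the plan says.** Protocol 7.2.1 sets 300 mg/dL as the lower limit for an individual and then narrows it: "More specifically, if any predose measurements show a reduction of IgG level to" that level or below, the individual rule is met. It adds: "Repeat testing to confirm the consistency of the result is permitted". It does not say whether dosing waits for the repeat.

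Protocol 4.2 gives the individual rule without a sampling time: "Dosing will be permanently stopped in any individual if the IgG level is reduced to" 300 mg/dL or below. The cohort rule in 7.2.1 has no sampling time either: "If 2 or more participants in a cohort exhibit IgG reduction to" that level, dosing in the cohort stops and escalation ends. Section 4.2 words the cohort rule in nearly the same way.

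Section 4.2 also promises: "To ensure a timely and adequate intervention if needed, IgG levels will be continuously and closely monitored during this study".

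Section 10.7.1.1 explains the entry criterion of at least 1,000 mg/dL. It reasons that falls are not expected to exceed about 70%, so IgG should stay above 300 mg/dL.

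**The concern.** An individual stopping rule in healthy volunteers should have one trigger and a defined time at which it acts. Here the trigger depends on which section is followed. Under 7.2.1 read literally, a participant with a post-dose value at or below 300 mg/dL may be dosed again. Under 4.2 that participant may not. Two such participants could stop their cohort although neither meets the individual rule in 7.2.1.

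Timing is a second gap. On most dosing days the only new IgG sample is drawn just before the infusion, and nothing requires its result, or any earlier one, to be reviewed first. At stake is a further weekly dose for someone who has already reached the threshold.

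**Working it through.** **Samples against doses** (Section 1.3, Tables 4 to 12).

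- Cohorts 4 to 6 are dosed on Days 1, 8, 15 and 22, so there are 4 − 1 = 3 repeat doses. Cohort 3 is dosed weekly from Day 1 to Day 78, so there are 12 − 1 = 11.
- After dose 1, all multiple-dose cohorts have post-dose IgG draws at 2, 4, 12, 24, 48, 72, 96, 120 and 144 hours, which is 9 samples before the Day 8 dose.
- Cohort 3 has the same 9 draws after the Day 22 dose, before dose 5 on Day 29. In Cohorts 4 to 6, Day 22 is the last dose.
- The 4.2 wording can therefore act earlier than 7.2.1 for 1 of 3 repeat doses in Cohorts 4 to 6 (dose 2) and 2 of 11 in Cohort 3 (doses 2 and 5).
- For the other 3 − 1 = 2 and 11 − 2 = 9 repeat doses, the only IgG sample since the previous dose is that day's predose draw. The two wordings then behave alike.
- In the single-dose cohorts there is no later dose for the individual rule to stop.

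**Time of action.** Section 1.3 puts blood sampling before study drug but does not ask for the result. Admission-day draws before repeat doses include no IgG. If the result is back before the infusion, no extra dose is given. If it comes back after that infusion but before the next one, 7 days later, one extra dose is given. The protocol states no turnaround. More than one extra dose would need a turnaround beyond a week, or dosing to continue while a repeat is awaited. The documents exclude neither, but give no sign of either.

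**Predicted levels** (Table 16 and Section 4.3). IgG remaining = baseline × (1 − fall), at the entry floor of 1,000 mg/dL:

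| Regimen | Predicted maximum fall | IgG remaining (mg/dL) |
|---|---|---|
| 1500 mg single (Cohort 1) | 45% | 550 |
| 2250 mg single (Cohort 2) | 48% | 520 |
| 750 mg × 12 (Cohort 3) | 68% | 320 |
| 1500 mg × 4 (Cohort 4) | 69% | 310 |
| 2250 mg × 4 (Cohort 5) | 72% | 280 |

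For Cohorts 4 and 5, Section 4.3 says "the expected maximum IgG reduction after 4 qw doses is expected to be around 69% and 72%, respectively", which is after their last dose. The time of the Cohort 3 nadir is not given, but 320 is above the threshold whenever it occurs. At dose 2 in Cohorts 4 and 5, the single-dose rows (550 and 520) suggest levels far from 300.

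**Section 10.7.1.1.** Fall needed to reach 300 from 1,000: 1 − 300/1,000 = 70%, and a value of exactly 300 meets the rule. Baseline at which a 72% fall gives 300: 300/(1 − 0.72) = 1,071 mg/dL. Baselines from 1,000 to 1,071 are therefore predicted to reach 300 or below in Cohort 5.

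**The case against.** Section 4.2 is design rationale and points to 7.2 for the stopping rules, so 7.2.1 is the operative text. It does not say that only predose values count. The sentence can be read as one sufficient condition, and the cohort rule as inheriting the same limit. Other provisions also let staff act on any low value:

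- dosing decisions after data review (6.6);
- immediate discussion of safety concerns with the sponsor (Section 8);
- moving PD sampling times (8.6);
- additional tests (10.2);
- an unblinded medical monitor (2.3.3, 10.7).

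The laboratory manual and the SRC charter were not available for this review and may set a turnaround. Section 10.7.1.1 argues that isolated IgG as low as 200 mg/dL would most likely leave a participant immunocompetent.

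Much of this stands. It limits the harm and shows that action is possible. It does not settle which samples count, and none of these provisions requires an IgG check before an individual's next dose. If the cohort rule did inherit the predose limit, the nadirs predicted for Cohorts 4 and 5, which fall after the last dose, could never count towards it.

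A reader might infer that the protocol predicts dosing of participants already at or below 300 mg/dL. It does not: the only prediction below 300, for Cohort 5, comes after the fourth and last dose. Nor do the documents support a probability of crossing. Table 16 footnote g says "IgG reduction at median body weight is presented", and no spread between individuals is given. The reported experience points both ways. This drug's earlier multiple-dose cohort fell by up to 64% (360 from 1,000), while in a study of another anti-FcRn agent "tIgG was decreased on average by approximately 75%, with some individuals showing reductions of up to 85" percent.

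**Conclusion.** The point holds, at minor severity. The two sections give different individual triggers, and neither a review of the latest result before infusion nor a hold during repeat testing is required. The choice of wording affects 1 of 3 repeat doses in Cohorts 4 to 6 and 2 of 11 in Cohort 3. The possible delay is one weekly dose, and it depends on a turnaround that the protocol does not state; it would be wrong to conclude that the rule must act late.

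The small practical effect rests on Table 16 predictions at median body weight and on the protocol's own case that 300 mg/dL is conservative. The margin in Cohort 3 is narrow, however: 70% against a predicted 68% at the entry floor.

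The error in 10.7.1.1 needs no assumption beyond the protocol's own figures. The entry criterion does not ensure that IgG stays above 300 mg/dL.

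The SAP (4.1) reports that the study was terminated early, so the correction now serves mainly the record and any later protocol that reuses this rule.

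**What to change.** 1. Amend 7.2.1 so that any IgG at or below 300 mg/dL after the first dose, predose or post-dose, triggers the individual stop. Allow a confirmatory repeat, with dosing held until it is back. Align 4.2, and say that the cohort rule counts the same values.
2. Require the unblinded medical monitor or the dedicated unblinded staff to check and document the most recent available IgG result before each infusion.
3. Correct 10.7.1.1: at 1,000 mg/dL a 70% fall already meets the rule, and the 72% fall predicted for Cohort 5 takes baselines of 1,000 to 1,071 mg/dL to 300 or below.

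The cost is wording plus a check of a result already on file, with no added visit or sample. The downside is that a held dose may be delayed or missed, with loss of that participant's PK and PD data for it. Step 2 does not remove the lag where the newest result is still pending, but it ensures that a known low value is not overlooked.
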